3. SUBJECT SELECTION

3.1 Study Population

Subjects who have documented progressive metastatic CRPC disease, who meet the inclusion and exclusion criteria will be eligible for participation in this study.

3.2 Inclusion Criteria

1. Histologically or cytologically confirmed adenocarcinoma of prostate
2. Documented progressive metastatic CRPC based on Prostate Cancer Working Group 3 (PCWG3) criteria, which includes at least one of the following criteria:
 - i. PSA progression
 - ii. Objective radiographic progression in soft tissue
 - iii. New bone lesions
3. ECOG performance status of 0–2
4. Have serum testosterone ≤ 50 ng/dL. Subjects must continue primary androgen deprivation with an LHRH/GnRH analogue (agonist/antagonist) if they have not undergone bilateral orchiectomy.
5. Have previously been treated with at least one of the following:
 - Androgen receptor signaling inhibitor (such as enzalutamide)
 - CYP 17 inhibitor (such as abiraterone acetate)
6. Have previously received taxane chemotherapy, been determined to be ineligible for taxane chemotherapy by their physician, or refused taxane chemotherapy.
7. Age ≥ 18 years
8. Patients must have normal organ and marrow function as defined below:
 - Absolute neutrophil count $\geq 2,000$ cells/mm³
 - Hemoglobin ≥ 9 g/dL
 - Platelet count $\geq 150,000 \times 10^9/\mu\text{L}$
 - Serum creatinine ≤ 1.5 x upper limit of normal (ULN) or calculated creatinine clearance ≥ 60 mL/min/1.73 m² by Cockcroft–Gault

- Serum total bilirubin $\leq 1.5 \times \text{ULN}$ (unless due to Gilbert's syndrome in which case direct bilirubin must be normal)
 - Serum AST and ALT $\leq 1.5 \times \text{ULN}$ in the absence of liver metastases; $< 3 \times \text{ULN}$ if due to liver metastases (in both circumstances bilirubin must meet entry criteria)
9. Ability to understand and the willingness to sign a written informed consent document.

3.3 Exclusion Criteria

1. Implantation of investigational medical device ≤ 4 weeks of Treatment visit #1 (Day 1) or current enrollment in oncologic investigational drug or device study
2. Use of investigational drugs ≤ 4 weeks or < 5 half-lives of Treatment visit # 1 (Day 1) or current enrollment in investigational oncology drug or device study
3. Prior systemic beta-emitting bone-seeking radioisotopes
4. Known active brain metastases or leptomeningeal disease
5. History of deep vein thrombosis and/or pulmonary embolus within 1 month of Treatment visit #1
6. Other serious illness(es) involving the cardiac, respiratory, CNS, renal, hepatic or hematological organ systems which might preclude completion of this study or interfere with determination of causality of any adverse effects experienced in this study
7. Radiation therapy for treatment of PC ≤ 4 weeks of Treatment visit #1
8. Patients on stable dose of bisphosphonates or denosumab, which have been started no less than 4 weeks prior to treatment start, may continue on this medication, however patients are not allowed to initiate bisphosphonate/Denosumab therapy during the DLT-assessment period of the study.
9. Having partners of childbearing potential and not willing to use a method of birth control deemed acceptable by the principle investigator and chairperson during the study and for 1 month after last study drug administration

10. Currently active other malignancy other than non-melanoma skin cancer. Patients are considered not to have “currently active” malignancy if they have completed any necessary therapy and are considered by their physician to be at less than 30% risk of relapse.
11. Known history of known myelodysplastic syndrome

4. OVERVIEW OF STUDY DESIGN AND METHODOLOGY

4.1 Study Design

This is an open-label, single-center Phase I dose-escalation study designed to determine the dose-limiting toxicity (DLT) and the maximum tolerated dose (MTD) of combination of ¹⁷⁷Lu-J591 and ¹⁷⁷Lu-PSMA-617 in a two-week dose-fractionation regimen. ¹⁷⁷Lu-J591 will be given at a moderate dose previously demonstrated to be safe x2 infusions two weeks apart. For ¹⁷⁷Lu-PSMA-617 the dose escalation will start at 3.7 GBq (100 mCi) and escalate in increments of 1.85 GBq (50 mCi) for each dose to a planned maximum of 9.25 GBq (250 mCi) x2 doses, 2 weeks apart. Should there be unacceptable toxicity at the initial dose level, we will de-escalate to dose level -1 (1.85 GBq / 50 mCi per dose). After the phase I study has established a MTD, the Phase II, single-arm trial will start.

Patients must have documented progressive metastatic CRPC disease based on Prostate Cancer Working Group 3 (PCWG3) criteria in order to be eligible for enrollment. Upon meeting the inclusion and exclusion criteria and signing the informed consent and HIPPA form, subjects will undergo the screening. As part of the screening, subjects will get a single dose of ⁶⁸Ga-PSMA-HBED-CC and will have a PET/CT. Nuclear Medicine physician(s) will review the PET/CT scans to document PSMA expression at tumor site(s).

Subjects will have Lutetium-177 Planar/SPECT Imaging on Day 8 (±1 day) after the first dose of ¹⁷⁷Lu-J591 + ¹⁷⁷Lu-PSMA-617. Optimal images will be performed on selected consenting subjects between the initial treatment visit #1 on Day 1 and Day 4 and prior to treatment visit #2 on D15 ±1. Subjects will be closely monitored for AEs (weekly x2 weeks, then every 2 weeks for one month, at 8 and 12 weeks, and then every 4 weeks for next 3 months).

Upon completion of investigational treatment with dose-fractionation regimen of the combination of ¹⁷⁷Lu-J591 + ¹⁷⁷Lu-PSMA-617, subjects will undergo ⁶⁸Ga-PSMA-HBED-CC injection and same day PET/CT at the end of study visit to document treatment response. Subsequently survival data and additional treatment(s) information will be captured from their routine Standard of care (SOC) visits.

Table 14: Phase I dose-escalation plan for combination of ¹⁷⁷Lu-J591 + ¹⁷⁷Lu-PSMA-617:

| ¹⁷⁷Lu–J591 + ¹⁷⁷Lu–PSMA–617: Dose escalation (per dose) | | |
|--|----------------------------------|----------------------------------|
| | ¹⁷⁷Lu–J591* | ¹⁷⁷Lu–PSMA–617 |
| | Dose: GBq (mCi) / m ² | Dose: GBq (mCi) |
| Cohort | | |
| -1 | 2.22 (60) | 1.85 (50) |
| 1 | 2.22 (60) | 3.7 (100) |
| 1a | 1.35 (36.5) | 3.7 (100) |
| 2 | 1.35 (36.5) | 5.55 (150) |
| 3 | 1.35 (36.5) | 7.4 (200) |
| 4 | 1.35 (36.5) | 9.25 (250) |

*Note: BSA will be capped at 2 for ¹⁷⁷Lu-J591 dosing.

Rationale for dosing amendment:

Prior studies of ¹⁷⁷Lu- and ⁹⁰Y-J591 have utilized individualize dosing per body surface area (BSA). As a single agent, ¹⁷⁷Lu-J591 when delivered in a 2-dose fractionated regimen is suggested to be dosed at 45 mCi/m² x2 (or 40 mCi/m² x2 with less toxicity and less efficacy). The dose in combination with docetaxel is 40 mCi/m² x2). In the initial version of the protocol, an estimate for fixed dosing based upon prior safe dose levels and average BSA was utilized. One subject in the initial cohort had prolonged myelosuppression and on analysis, had a low BSA. Therefore based upon the wealth of prior safety data with BSA dosing and the wish to primarily assess one rather than 2 dosing variables, the dosing amendment will revert to BSA dosing. In addition, we will cap BSA at 2 m² with the intent of minimizing myelosuppression from the RIT.

4.2 Phase I:

The Phase I portion will use a 3+3 dose-escalation study design, with the planned initial and subsequent cohorts described in Table 14. This study design is well-described and accepted by the clinical and scientific community, so we will not provide complete details here. Briefly, this design is constructed to reduce the chance of escalating the dose when the probability of DLT is high, and increase the chance of escalating the dose when the probability of DLT is low. The MTD is defined as the highest dose level with an observed incidence of DLT in no more than one out of six patients treated at a particular dose level. The dose escalation scheme provides the following probabilities of escalation based on the true chances of DLT at a specific dose level. One can see that the probability of escalation is high if the toxicity risks are low:

| | | | | | | | |
|-------------------------------|-----|-----|-----|-----|-----|-----|-----|
| True Probability of Toxicity: | .05 | .10 | .20 | .30 | .40 | .50 | .60 |
| Probability of Escalation: | .97 | .91 | .71 | .49 | .31 | .17 | .08 |

As there is a reasonably large pool of short- and long-term experience with PSMA-directed ¹⁷⁷Lu, a phase II trial using the MTD to will be launched to obtain preliminary efficacy data.

4.3 Phase II:

We will enroll up to 27 subjects in the Phase II trial utilizing a Simon two-stage design (including the 3-6 patients used for establishing the MTD). For the phase II portion, we will define evaluable patients as those who met eligibility requirements, have initiated therapy, and were not removed from the study for non-compliance or withdrawal. Sample size recommendations for the two-stage design are determined according to Simons two-stage minimax design. The first stage will accrue a total of 16 patients (including those who were treated at the MTD in the phase I portion), if 6 or fewer of the first 16 evaluable patients do not experience a 30% decline in PSA, the study will be terminated and declared to have a negative result. If 7 or more patients out of the first 16 evaluable patients experience a 30% decline in PSA, 9 more patients will be accrued in Stage 2 (total sample size of 27). The new regimen will be declared to have activity and be worthy of further testing if 13 or more patients experience a 30% PSA decline among the 27 patients who are part of the phase II trial.

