| Study Design: | Phase I dose escalation study with combination of ^{177}Lu -J591 and ^{177}Lu -PSMA-617 using a dose-fractionated regimen will be performed in patients with documented progressive metastatic CRPC. The cumulative ^{177}Lu-J591 dose for each subject will be 2.7 GBq/m² (73 mCi/m²) of ^{177}Lu with 20 mg J591 and the cumulative ^{177}Lu-PSMA-617 dose for each subject will vary (depending on the Cohort) from 3.7 GBq (100 mCi) to 18.5 GBq (500 mCi). The ^{177}Lu -PSMA-617 dose will be escalated in up to 6 different dose levels (3+3 dose-escalation study / de-escalation design). For the phase II portion, a minimum number of 14 patients will be enrolled at MTD (including those enrolled at MTD in Phase I) and a maximum of 24. |
| Study Duration: | Approximately 3 months after enrollment, then transition to long-term follow up |
| Study Agent: | 1) ^{177}Lu -PSMA-617 [1.85 GBq (50 mCi) – 9.25 GBq (250 mCi)] x2 doses, 2 weeks apart (Treatment Visit #1 and #2), IV administration 2) ^{177}Lu -J591 [1.35 GBq/m ² or 36.5 mCi/m ²] x2 doses, 2 weeks apart (Treatment Visit #1 and #2), IV administration 3) ^{68}Ga -PSMA-HBED-CC [185 \pm 74 MBq or 5 \pm 2 mCi] intravenous during screening and at 12 weeks (\pm 1 week) with standard imaging |
| Primary Objectives: | 
(Phase I) Determine the dose limiting toxicity (DLT) of dose-fractionated combination therapy with ^{177}Lu-J591 and ^{177}Lu-PSMA-617 |

- (Phase I) Determine the maximum tolerated dose (MTD) and recommended phase II dose (RP2D) of dose-fractionated combination therapy with ^{177}Lu -J591 and ^{177}Lu -PSMA-617
 - (Phase II) To assess the proportion with PSA decline following the dose-fractionated combination therapy with ^{177}Lu -J591 and ^{177}Lu -PSMA-617
- Secondary Objectives:**
- To assess radiographic response rate by RECIST 1.1 with PCWG3 modifications
 - To assess biochemical and radiographic progression-free survival by PCWG3 criteria
 - To assess overall survival following the dose-fractionated combination therapy with ^{177}Lu -J591 and ^{177}Lu -PSMA-617
 - To assess safety of dose-fractionated combination therapy with ^{177}Lu -J591 and ^{177}Lu -PSMA-617 as assessed by CTCAE 4.0
 - To assess changes in CTC count as measured by CellSearch and the rate of favorable CTC count and LDH at 12 weeks following dose-fractionated combination therapy with ^{177}Lu -J591 and ^{177}Lu -PSMA-617

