6.2.4 Dose levels for ^{177}Lu -J591 + ^{177}Lu -PSMA-617

Subject(s) enrollment will be done as 3+3 study design at each dose level. Initially at least 3 subject(s) will be enrolled in Cohort 1 and will receive ^{177}Lu -PSMA-617 (2 GBq or 54 mCi x2 doses 2 weeks apart) with dose escalation as described above in **Section 4.1 (Table 14)**.

Simultaneously, all subjects will receive in combination a fixed dose of ^{177}Lu -J591 (1.35 GBq/m² or 36.5 mCi/m² capped at BSA of 2) x2 doses, 2 weeks apart. The enrollment ceiling of the dose escalation portion of the study is up to 30 treated study participants (up to five groups, up to 6 at each dose level). Each patient would receive two doses of both investigational agents (^{177}Lu -J591 and ^{177}Lu -PSMA-617) in combination 2 weeks apart. The total dose received by a subject will vary from **4 GBq/m² (108 mCi/m²) to 20 GBq/m² (540 mCi/m²)** for ^{177}Lu -PSMA-617. The total dose received by a subject for ^{177}Lu -J591 will be **2.7 GBq/m² (73 mCi/m²)**, with BSA capped at 2.

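### The dose-escalation table in 4.1 still gives J591 as 2.22 GBq (60 mCi) at de-escalation level -1, against 1.35 GBq/m² for every subject elsewhere; read as a flat dose, it gives low-BSA men no marrow relief

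*Combined protocol and SAP*

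**What the plan says.** The dose-escalation table in section 4.1 (one of two tables numbered 14) heads its J591 column in GBq (mCi) per m². Under the table is the note "BSA will be capped at 2 for" J591 dosing. Two of its rows matter here:

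- Level -1, after its minus sign: "1 | 2.22 (60) | 1.85 (50" (level, J591, PSMA-617).
- Cohort 1a, the first row on the amended J591 dose: "1a | 1.35 (36.5) | 3.7 (100".

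Cohort 1 carries the same 2.22 (60) as level -1. Cohorts 2 to 4 carry 1.35 (36.5). Section 4.1 keeps level -1 in use: after unacceptable toxicity at the initial level, "we will de-escalate to dose level -1 (1.85 GBq / 50 mCi per dose". That sentence gives only a PSMA-617 activity.

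Elsewhere the J591 dose has no exception. The Protocol Summary says the cumulative J591 "dose for each subject will be 2.7 GBq/m² (73 mCi/m²". Section 6.2.4 gives all subjects "1.35 GBq/m² or 36.5 mCi/m² capped at BSA of 2) x2 doses".

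The rationale under the table explains the history. In the initial protocol "an estimate for fixed dosing based upon prior safe dose levels and average BSA was utilized". Then "One subject in the initial cohort had prolonged myelosuppression and on analysis, had a low BSA", and J591 went back to BSA dosing so that only one dosing variable would mainly be assessed.

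**The concern.** Level -1 is used only after unacceptable toxicity, and section 2.8 expects red marrow to be the dose-limiting tissue for J591. A de-escalation step should therefore not raise J591 or leave marrow exposure unchanged. The table gives level -1 a J591 entry that conflicts with the summary and 6.2.4, and nothing says which text prevails. Section 7 has each man receive both agents according to his assigned dose level or cohort, so a pharmacist working from the table could prepare 60 mCi. In a man of low BSA that is more J591 than the level he was moved down to avoid.

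A smaller defect sits in 6.2.4. It states Cohort 1 PSMA-617 as 2 GBq (54 mCi) per dose and a cumulative range of 4 to 20 GBq/m². Section 4.1 gives 3.7 GBq (100 mCi) per dose, and the summary gives a flat cumulative 3.7 to 18.5 GBq.

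**Working it through.** **The plan's own figures.** With 1 mCi = 0.037 GBq, 36.5 mCi = 1.35 GBq. Two doses give 2 × 1.35 = 2.7 GBq/m² and 2 × 36.5 = 73 mCi/m², as the summary states. Also 60 × 0.037 = 2.22, so the level -1 entry converts correctly. What is in doubt is its unit and its currency.

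**Does the summary's statement cover level -1?** Yes. Its cumulative PSMA-617 range starts at 3.7 GBq. Cohort 1 and 1a give 2 × 3.7 = 7.4 GBq, and only level -1 gives 2 × 1.85 = 3.7 GBq. The same sentence sets J591 at 73 mCi/m², so the conflict is direct.

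**J591 per dose, level -1 read as a flat 60 mCi, against Cohort 1a (36.5 × BSA).**

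| BSA | Level -1 | Cohort 1a | Ratio |
|---|---|---|---|
| 1.5 m² | 60 | 54.75 | 1.10 |
| 1.64 m² (60/36.5) | 60 | 60 | 1.00 |
| 2.0 m² | 60 | 73 | 0.82 |

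The 1.5 m² is illustrative. The 2.0 m² is the average-person BSA used in the J591 dosimetry text of section 2.6.

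**Marrow dose from both agents, both infusions.** Inputs are J591 at 1.17 rad/mCi (Table 8) and PSMA-617 at 0.03 mGy/MBq (2.4.1, item d), with 10 mGy = 1 rad. Check on the first coefficient: 70 mCi/m² × 2.0 m² × 1.17 = 163.8, the 164 rads printed in 2.6.

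- Level -1, flat: 120 × 1.17 + 3,700 × 0.03/10 = 140.4 + 11.1 = 151.5 rad at any BSA.
- Cohort 1a at 1.5 m²: 109.5 × 1.17 + 7,400 × 0.03/10 = 128.1 + 22.2 = 150.3 rad.
- Level -1 with J591 corrected to 36.5 mCi/m², at 1.5 m²: 128.1 + 11.1 = 139.2 rad, 7% below 1a.
- Cohort 1a at 2.0 m²: 146 × 1.17 + 22.2 = 193.0 rad.

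So at 1.5 m² the printed row gives no reduction, while the corrected row gives a modest one. At 2.0 m² the flat reading does lower marrow dose, 151.5 against 193.0. Using the Table 2 mean of 0.034 mGy/MBq instead of the rounded 0.03, the 1.5 m² comparison becomes 140.4 + 12.6 = 153.0 against 128.1 + 25.2 = 153.3, which is still no material reduction.

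**Level -1 read literally per m².** Cumulative J591 is 2 × 60 = 120 against 73 mCi/m², a ratio of 1.64 at every BSA. It is 120/90 = 1.33 times the highest fractionated recommended dose (45 mCi/m² × 2). At 2.0 m² the marrow estimate is 240 × 1.17 + 11.1 = 291.9 rad.

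**PSMA-617 in 6.2.4.** 54/100 = 0.54, so the stated Cohort 1 dose is 46% too low. The range ends are 4/3.7 = 20/18.5 = 1.081, or 8.1% too high, and carry a per-m² unit that does not belong.

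**The case against.** The strongest reply is that the rest of the protocol makes the intended dose plain. The summary and 6.2.4 give one J591 dose for all subjects. The de-escalation sentence changes PSMA-617 only, and the amendment aims to vary one agent. The treatment-visit list in 6.1.2.1 attaches its cohort qualifier to PSMA-617 alone. All of this points to 36.5 mCi/m² at level -1, and it stands as evidence of intent. It does not remove the conflict: section 7 ties both agents to the assigned level, and the table is where that level is defined.

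A reader might infer from the column header that the protocol would give 60 mCi/m² twice, a 64% increase in every man who de-escalates. In its favour, 2.3.1.2 links repeat dosing at 45 to 60 mCi/m² with dose-limiting myelosuppression. But the text directly under the table puts the single-agent fractionated dose at 40 or 45 mCi/m² and says the initial protocol used fixed dosing. Section 4.1 calls the J591 dose moderate and previously shown to be safe. The documents therefore support a leftover flat dose far better than a planned 120 mCi/m².

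On the flat reading the objection has more force. Men above 1.64 m² would receive less J591 than in Cohort 1a. At 1.5 m² the flat dose equals 60/1.5 = 40 mCi/m², a recommended single-agent fractionated dose, though not one established in this combination. The documents give no BSA distribution, so how many men fall below 1.64 m² is unknown.

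The 6.2.4 figures might also be read as a misdosing risk. That is too strong: 6.2.4 itself sends the reader to the table in 4.1, and Cohort 1 appears already treated.

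**Conclusion.** The level -1 J591 entry is wrong as written, because it contradicts the dose stated for every subject in two other places. On the likelier, flat reading the effect is moderate and depends on BSA: 10% more J591 per dose than Cohort 1a at 1.5 m², parity at 1.64 m², and 18% less at 2.0 m². For men of low BSA, de-escalation would bring no fall in estimated marrow dose (151.5 against 150.3 rad at 1.5 m²). The literal per-m² reading would be far worse, but the documents do not support treating it as the intended dose.

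This rests on three assumptions: the flat origin is inferred from the amendment rationale, 1.5 m² is illustrative, and mean marrow coefficients are held constant across BSA. The error matters only if the trial de-escalates. No sample size, power or error rate depends on it. It still needs correcting before anyone is treated at level -1, because it is an activity of a myelosuppressive agent in the row reserved for use after toxicity. The 6.2.4 discrepancy is a minor text correction.

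**What to change.** - In the 4.1 dose-escalation table, set level -1 J591 to 1.35 GBq/m² (36.5 mCi/m², BSA capped at 2 m²).
- Label the Cohort 1 J591 entry as the pre-amendment dose and give its true unit.
- In 6.2.4, state the starting PSMA-617 dose as 3.7 GBq (100 mCi) × 2 and the cumulative range as a flat 3.7 to 18.5 GBq (100 to 500 mCi). Alternatively, replace these figures with a reference to the dose-escalation table in 4.1, cited by section because two tables share the number 14.

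The cost is a wording amendment, with no added patients or procedures.

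### Table 14 prints a J591 dose of 60 mCi under a per-m² heading for de-escalation level −1, against the 36.5 mCi/m² stated for every subject

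*Combined protocol and SAP*

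**What the plan says.** Table 14 in section 4.1 lists doses per infusion, and the unit of its J591 column is GBq (mCi) per m². From the digit of the cohort label onward, the Cohort −1 row reads "1 | 2.22 (60) | 1.85 (50" and the Cohort 1 row "1 | 2.22 (60) | 3.7 (100". Cohorts 1a to 4 all carry 1.35 (36.5). The only note to the table concerns the cap ("Note: BSA will be capped at 2 for" J591 dosing). Nothing marks a row as flat or historical.

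The rationale below the table explains the history: "In the initial version of the protocol, an estimate for fixed dosing based upon prior safe dose levels and average BSA was utilized". It adds: "One subject in the initial cohort had prolonged myelosuppression and on analysis, had a low BSA". For that reason, and from "the wish to primarily assess one rather than 2 dosing variables, the dosing amendment will revert to BSA dosing". It does not say which J591 dose or unit now applies at level −1.

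The de-escalation rule in section 4.1 is still current. After unacceptable toxicity at the initial dose level, "we will de-escalate to dose level -1 (1.85 GBq / 50 mCi per dose"). That figure is the PSMA-617 dose; the sentence gives none for J591.

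Elsewhere the J591 dose is uniform. The Protocol Summary gives each subject 36.5 mCi/m² twice, a cumulative 73 mCi/m² (2.7 GBq/m²). Section 6.2.4 gives all subjects the same, with BSA capped at 2.

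**The concern.** Level −1 is where the trial goes when the starting combination has proved too toxic. Section 2.8 expects red marrow to be the dose-limiting tissue for J591. Because the de-escalation sentence names only PSMA-617, whoever prepares a level −1 dose must take the J591 figure from Table 14, and section 7 doses patients by assigned cohort. The table shows a larger number there than in the cohorts above it, under a heading that makes it per m².

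Taken literally, de-escalation would raise the marrow-toxic agent for everyone coming from Cohort 1a. Taken as a flat dose, it would still raise it in men of small BSA, and low BSA is the feature the rationale reports in the patient with prolonged myelosuppression.

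A second, lesser consequence is that a step from 1a to −1 would change both agents. A better or worse result could then not be put down to PSMA-617 alone, although the amendment was meant mainly to study one dosing variable.

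**Working it through.** **Inputs.** J591 at level −1: 60 mCi (Table 14). J591 for every subject: 36.5 mCi/m² twice (Protocol Summary; section 6.2.4, BSA capped at 2). Fractionated single-agent doses: 40 or 45 mCi/m² twice (sections 2.3.1.2 and 4.1). Average BSA used for dosimetry: 2.0 m²; mean marrow dose: 1.17 rads/mCi (section 2.6). Conversion: 1 mCi = 0.037 GBq.

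**The plan's own figures.** 2 × 36.5 = 73 mCi/m², and 73 × 0.037 = 2.70 GBq/m², which matches the stated cumulative dose. 60 × 0.037 = 2.22 GBq, so the table's conversion is right. The fault lies in which dose and unit apply.

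**Does the 36.5 mCi/m² rule cover level −1?** The Protocol Summary starts the PSMA-617 range at 50 mCi per dose and 100 mCi cumulative (2 × 50). In Table 14 those values occur only in Cohort −1. The Summary therefore includes that level, and it lists no J591 dose other than 36.5 mCi/m².

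**Reading 1: per m², as headed.**
- Ratio: 60 / 36.5 = 1.64, an increase of 64%.
- Cumulative: 2 × 60 = 120 mCi/m², against 73.
- Against the fractionated single-agent doses: 120 / 90 = 1.33 and 120 / 80 = 1.50, so 33% to 50% above.
- Mean marrow dose from J591 alone at BSA 2.0: 1.17 × 240 mCi = 281 rads, against 1.17 × 146 mCi = 171 rads. Section 2.6 puts the tolerable marrow dose at about 3.0 Gy.

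**Reading 2: flat 60 mCi.** The comparator per infusion is 36.5 × min(BSA, 2). The two are equal at BSA = 60 / 36.5 = 1.64 m².

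| BSA (m²) | 36.5 mCi/m² gives (mCi) | Flat 60 mCi, change | Flat 60 as mCi/m² |
|---|---|---|---|
| 1.5 | 54.8 | +9.6% | 40.0 |
| 1.6 | 58.4 | +2.7% | 37.5 |
| 1.64 | 59.9 | about 0 | 36.6 |
| 1.8 | 65.7 | −8.7% | 33.3 |
| 2.0 | 73.0 | −17.8% | 30.0 |

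BSA values other than 2.0 are illustrative. Above 2.0 m² the cap holds the change at −17.8%.

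**Which reading is likelier?** The rationale says the initial protocol used fixed dosing built from safe levels and an average BSA. At 2.0 m², 60 / 2.0 = 30 mCi/m², a level that section 2.3.1.2 reports could be given safely up to three times. This fits a leftover flat dose, but the documents do not say so. It is an inference, and the conflict does not depend on it.

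**Starting point.** These comparisons are with Cohort 1a. From Cohort 1, which carries the same printed figure, J591 would not change.

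**The case against.** The strongest reply is that harm on the likelier reading is small. The protocol says single-agent fractionated J591 "is suggested to be dosed at 45 mCi/m² x2 (or 40 mCi/m² x2 with less toxicity and less efficacy"). A flat 60 mCi exceeds 40 mCi/m² only below 60 / 40 = 1.5 m², and 45 mCi/m² only below 60 / 45 = 1.33 m². At 2.0 m² it is a reduction. This stands, and it limits the concern. It does not remove it, because the single-agent doses were not given with PSMA-617.

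The literal reading would also be hard to act on. The rationale under the table mentions fixed dosing, section 4.1 describes the J591 dose as moderate and already shown to be safe, and section 6.2.4 gives 36.5 mCi/m², so staff would have grounds to query the row. That makes an actual overdose less likely but leaves the dose table wrong. Section 6.2.4 is also an imperfect safeguard: its PSMA-617 dose for Cohort 1 (54 mCi) disagrees with Table 14 (100 mCi).

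The row is used only if toxicity occurs, and level −1 might have belonged to the original Cohort 1 alone. Against that, section 4.1 and the lower bounds in the Protocol Summary keep it available.

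Finally, a 3+3 de-escalation need not attribute its result to one agent, and the sponsor might have wanted a lower J591 dose at −1. The attribution point is indeed secondary. An intended lower dose is possible, but the current text states none.

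**Conclusion.** The inconsistency is real and must be corrected before level −1 is used. The J591 entry for Cohort −1 conflicts with the only J591 dose that the current text gives for all subjects, and nothing in the documents resolves it. The per-m² reading is an upper bound: +64%, or 120 against 73 mCi/m² cumulative. The likelier flat reading runs from about +10% at 1.5 m², through no change at 1.64 m², to −18% at 2.0 m² and above. This is a wrong dose figure at a level that remains live, not a certain overdose.

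The sizes assume that Cohort 1a is the initial dose level after the amendment, and they use illustrative BSA values below 2.0 m². The same figure in Cohort 1 appears to record a dose already given and is mainly a labelling fault.

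**What to change.** 1. In Table 14, change the Cohort −1 J591 cell to 1.35 (36.5) per m², with BSA capped at 2, to match the Protocol Summary and section 6.2.4. If the sponsor did intend a different J591 dose at this level, it should state that dose with its unit and amend those two places to agree.
2. Label the Cohort 1 J591 cell as a historical flat dose of 2.22 GBq (60 mCi) per infusion, after checking the unit against the initial protocol version.
3. In the de-escalation sentence of section 4.1, give the J591 dose beside the PSMA-617 dose: 1.35 GBq/m² (36.5 mCi/m²), BSA capped at 2.

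The cost is two table cells and one sentence. No patients, visits or procedures are added.

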12.2. Phase II Study Design/Endpoints

We will enroll up to 27 subjects into the Phase II portion (including the 3-6 used for establishing the MTD). We will define evaluable patients as patients who met eligibility requirements, have initiated therapy, and were not removed from the study for non-compliance or patient withdrawal.

Sample size recommendations for the two-stage design are determined according to Simon's two-stage minimax design. We project a 30% PSA decline proportion of 35%, below which the regimen will be unacceptable and a 30% PSA decline proportion of 60%, above which the regimen will be considered worthy of further exploration. The null hypothesis that the 30% PSA decline proportion is less than or equal to 35% will be tested against the alternative hypothesis that the 30% PSA decline proportion is greater than or equal to 60%.

The sample size computations were performed assuming a 0.10 one-sided level of significance and 90% power assuming a historical control value for PSA decline of 35% and the alternative

hypothesis of 60%. If 6 or fewer of the first 16 evaluable patients do not experience a 30% decline in PSA (stage 1), the study will be terminated and declared to have a negative result. If 7 or more patients out of the first 16 evaluable patients experience a 30% decline in PSA, ongoing accrual will proceed to the target sample size of 27 patients (stage 2). The new regimen will be declared active in this patient population and worthy of further testing if 13 or more patients experience a 30% PSA decline among the 27 patients entered. This two-stage design yields a 0.90 probability of a positive result if the true 30% PSA decline proportion is 60%. It yields a 0.90 probability of a negative result if the true 30% PSA decline proportion is 35%. An exact 95% binomial confidence interval will be constructed for the proportion of patients with PSA decline.

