12.6 Interim Analysis

No interim analysis is planned for the phase I portion (though safety analyses will occur in real-time and prior to each dose-escalation). For the phase II portion, accrual will be suspended

after 16 patients have been enrolled in stage 1. If at least 7 patients out of the 16 patients experienced a PSA decline > 30%, 9 more patients will be accrued as part of stage 2.

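### Phase II decision rules contradict their own Simon design: stage 2 adds 9 patients where 11 are needed, and the stage 1 stopping sentence is inverted

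*Combined protocol and SAP*

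**What the plan says.** **Stage 2 size.** Section 4.3 sets a first stage of 16, which already includes Phase I patients treated at the MTD, and then states "9 more patients will be accrued in Stage 2 (total sample size of 27" (in parentheses). Section 12.6 Interim Analysis suspends accrual "after 16 patients have been enrolled in stage 1. If at least 7 patients out of the 16 patients experienced a PSA decline" above 30%, then adds the same 9. Section 12.2 gives no increment: "ongoing accrual will proceed to the target sample size of 27 patients (stage 2". Its success rule is "13 or more patients experience a 30% PSA decline among the 27 patients entered".

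The Protocol Summary (Sample Size row) and section 12.3 give 16 to 27 for Phase II. The summary's Study Design row gives 14 to 24.

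**Stage 1 stopping.** Section 4.3: "if 6 or fewer of the first 16 evaluable patients do not experience a 30% decline in PSA, the study will be terminated" and declared negative. Section 12.2 has the same condition: "If 6 or fewer of the first 16 evaluable patients do not experience a 30% decline in PSA (stage 1". In both sections the next sentence continues the trial when 7 or more of the 16 do have the decline.

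**Design inputs (12.2).** Simon two-stage minimax, null 35%, alternative 60%, one-sided 0.10, power 90%.

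**The concern.** These sentences are the operative rules for the Phase II primary objective, and they fail in two ways.

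- **Size.** The only two places that state an increment both lead to 25 patients, while the success cut-off and the claimed power belong to 27. Staff following 4.3 or 12.6 could close accrual two patients early, at a size for which the plan has no cut-off.
- **Direction.** Both places that state the termination rule attach it to the wrong event. With 10 to 16 responders the text orders termination and continuation at once. With 0 to 6 responders, 12.6 leaves accrual suspended, but no sentence says that the study then ends as negative.

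**Working it through.** **Inputs.** p0 = 0.35, p1 = 0.60, alpha 0.10 one-sided and power 0.90 (12.2); n1 = 16, continue with ≥7 responders (4.3, 12.2, 12.6); N = 27, success with ≥13 (4.3, 12.2).

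**Formula.** With X1 ~ Bin(16, p) and X2 ~ Bin(N − 16, p) independent, and c the success cut-off,

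P(positive) = Σ over x = 7 to 16 of P(X1 = x) × P(X2 ≥ c − x).

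**1. Reproduce the stated design (N = 27, c = 13, stage 2 = 11).**
- p = 0.35: P(positive) = 0.0979, so P(negative) = 1 − 0.0979 = 0.902 (stated 0.90).
- p = 0.60: P(positive) = 0.9001 (stated 0.90).
- Early stopping, P(X1 ≤ 6): 0.688 at 0.35 and 0.058 at 0.60.
- Expected N at 0.35: 16 + (1 − 0.688) × 11 = 19.4.

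An exhaustive search over designs from N = 10 upward finds 27 to be the smallest total with alpha ≤ 0.10 and power ≥ 0.90. At 27, the design with the lowest expected size under the null is n1 = 16, stop at ≤6, success at ≥13. So 12.2 is the minimax design it claims to be, and stage 2 must be 27 − 16 = 11.

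**2. Totals other than 27, same first stage (16, continue with ≥7).**

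| Total N | Cut-off | Alpha (p = 0.35) | Power (p = 0.60) |
|---|---|---|---|
| 27 | 13 | 0.098 | 0.900 |
| 25 (16 + 9) | 13 | 0.058 | 0.836 |
| 25 (16 + 9) | 12 | 0.112 | 0.8997 |
| 24 (Study Design row) | 13 | 0.041 | 0.783 |
| 24 (Study Design row) | 12 | 0.088 | 0.872 |

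The plan contains only the cut-off of 13. The rows with 12, and the pairing of 24 with a 16-patient first stage, are assumptions made to show the range. No row below 27 meets both limits.

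**3. The stopping sentence read literally.** Six or fewer non-responders among 16 means 16 − 6 = 10 or more responders.
- P(X1 ≥ 10): 0.527 at p = 0.60 and 0.023 at p = 0.35. This is how often the sentence conflicts with the one after it.
- If the sentence were obeyed, so that only 7 to 9 responders led to stage 2 (N = 27, c = 13), P(positive) at p = 0.60 would be 0.374.
- P(X1 ≤ 6), where no sentence declares a negative result: 0.688 at 0.35 and 0.058 at 0.60.

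**4. Can the 9 be explained otherwise?** Not by Phase I patients at the MTD: 4.3 already counts them in the 16. Not by the Study Design row: 24 − 14 = 10.

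**The case against.** The strongest reply is that nobody would be misled. The total of 27 stands in the same sentence as the 9 and recurs in 12.2, 12.3 and the summary. The continuation sentence and 12.6 both point the right way. With 0 to 6 responders accrual is already halted, and 13 of 27 cannot be reached, so only a label is missing; the claimed 0.90 probability of a negative result at 35% reproduces only if those outcomes count as negative. On this view 0.53 is the chance that two sentences collide, not the chance of a wrong stop, and a loss of power at 25 presumes that 13 is kept as the cut-off.

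Most of this is fair. The intent can be recovered, and 0.53 should be read as a collision rate. The power figure does depend on keeping 13, but the alternative is no better: with 12 of 25, alpha exceeds 0.10 and power falls marginally short. The operating characteristics at 24 depend on assumed pairings and are only illustrative.

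Two side remarks are also right. Sections 4.3 and 12.2 count evaluable patients while 12.6 counts enrolled ones, and the ceiling of 57 (30 + 27) is weak support for 27, because Phase II includes the MTD patients from Phase I and 12.3 caps Phase I at 24. Neither changes the conclusion. What remains is that a primary decision rule should not have to be reconstructed from its operating characteristics.

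**Conclusion.** The point holds, and it must be fixed. The sample-size calculation is correct; the rules written around it are not. Stage 2 needs 11 patients, not 9, and the termination sentence in 4.3 and 12.2 says the reverse of what the design requires.

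The practical risk is closure at 25. With the plan's only cut-off (13), power falls from 0.900 to 0.836 and alpha from 0.098 to 0.058, a loss of power and not of false-positive control. With 12, alpha rises to 0.112. Either way the stated properties fail. The inverted sentence contradicts the continuation rule with probability 0.53 at a true rate of 60%, and the negative declaration is missing for the outcome that has probability 0.69 at 35%.

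These figures assume independent binomial responses, full evaluability, and the 35% and 60% rates in 12.2. The two contradictions in the text need no assumption.

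**What to change.** - **4.3 and 12.6 Interim Analysis:** replace the stage 2 increment of 9 with 11 (16 + 11 = 27). Wording the target as 27 evaluable patients would also settle the evaluable-versus-enrolled difference.
- **4.3 and 12.2:** write: if 6 or fewer of the first 16 evaluable patients have a PSA decline of at least 30%, the study is terminated and declared negative.
- **Protocol Summary, Study Design row:** change 14 and 24 to 16 and 27.
- **12.6 Interim Analysis, for consistency only:** change the threshold from above 30% to at least 30%, as in 10.2.

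The cost is a wording amendment. The Phase II total of 27 is already planned and lies within the accrual ceiling of 57; no calculation, cut-off or clinical procedure changes.
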